#### 6.1.5.2. 24 Hr Uox Measurements Which Do Not Meet Completeness Criteria

To maintain the integrity of all analyses related to 24-hour Uox measurement, urine completeness criteria have been established to ensure adequate, valid collection of all 24-hour Uox samples.

##### **Screening Period 24-hour Urine Collection Completeness:**

According to the protocol, there must be no more than 20% variation between the two 24-hour urinary creatinine values measured in the screening period. Should the initial pair of screening values not meet this criterion, participants will be given the opportunity to perform a second pair of collections. The screening period may be extended by 7 days (for a total of 42 days in screening) to allow time to repeat the additional 24-hour urine collections. Additionally, the site will review the 24-Hour Urine Collection Schedule worksheets completed by the participant. Any collection with a duration of less than 22 hours or greater than 26 hours will be considered invalid and must be repeated.

##### **Treatment Period 24-hour Urine Collection Completeness:**

As detailed in the Study Unblinded Clinical Monitoring Plan, certain members of the unblinded study team will conduct an ongoing review of treatment-period 24-hour urinary creatinine excretion values, to ensure all weight-adjusted 24-hour urinary creatinine excretion values are no more than 20% of baseline. If the percentage change in any weight-adjusted 24-hour urinary creatinine excretion values are more than 20% of baseline, then this is a violation of the completeness criteria. If weight is missing at a visit, LOCF (last observation carry forward) weight should be used in creatinine excretion values per kg calculation. Baseline is defined as the mean of the 2 screening values. Additionally, the site will review the 24-Hour Urine Collection Schedule worksheets completed by the participant. Any collection with a duration of less than 22 hours or greater than 26 hours will be considered invalid.

Should a treatment-period value not meet these criteria, participants will be required to complete another 24-hour urine collection. Recollection should occur within 10 calendar days from the time of the visit for which the collection was intended whenever possible. In the event the repeated 24-hour urine collection violates the completeness criteria, the 24-hour urine collection for that visit will not be repeated a second time.

For the analyses of AUC related endpoints, only 24 hour urine oxalate measurements that meet the completeness criteria will be used for each visit to calculate AUC. That usually would be the latest measurement in case of recollection if criteria are not met. In case there is more than one measurement that does not violate the completion criteria, the average will be taken.

Measurements that violate the completeness criteria will not be included in the AUC calculations. Rather those values will be treated as missing data and will be imputed via the MI methods described in section 6.1.5.1 prior to calculating the AUC values for analysis.

As a sensitivity analysis, when there is no measurement that meets completeness criteria for that visit, if the changes from baseline of both 24-hour urinary creatinine excretion values go in the same direction (i.e., positive or negative), then the 24-hour Uox measurement with the smallest absolute change will be used; otherwise, if they go in different direction, then the 24-hour Uox measurement with the positive change from baseline of 24-hour urinary creatinine excretion will be used. The conservative approach is to refrain from observing any effect due to an under-collection

### **6.1.6. Uox Measurements below the Limit of Quantitation**

If a reported Uox measurement is below the limit of quantification (LLOQ), then the 24 hour Uox value will be imputed as 0. For oxalate values < 50 umol/L, the 24 hour Uox value will be imputed as 0 umol/24h.

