 - p. Participants should maintain consistent fluid intake (i.e., hyperhydration) over the course of the study (Section **5.3**). Participants will report average daily fluid intake over the 4 to 7 days prior to each 24-hour urine collection (Section **8.2.7**).

- q. On Days 1 and 30, ECG to be performed predose and at 10 hours (\pm 30-minutes) postdose. A single ECG to be performed at other visits, as indicated (Section 8.2.5). If multiple assessments are due at the same time point, PK sampling should be performed preferably at the nominal time point, with the preferred order of assessments ECG, vitals, PK, and then other assessments.
- r. Vital signs on Day 1 and Day 30 to be assessed predose and at 10 hours (\pm 30-minutes) postdose (Section 8.2.3). If multiple assessments are due at the same time point, PK sampling should be performed preferably at the nominal time point, with the preferred order of assessments ECG, vitals, PK, and then other assessments.
- s. A full physical exam will be performed at Screening and Day 180 (or ET). A brief physical examination may be performed at other scheduled visits (Day 1 through Day 150) or unscheduled visits at the Investigator's discretion. See Sections **8.2.1** and **8.2.2**.
- t. In participants \geq 18 years of age, height to be recorded only at screening. In participants $<$ 18 years of age, height will be recorded at specified visits for calculation of eGFR and BSA adjustment of U_{ox} excretion. Weight to be recorded in all participants at specified visits. In participants aged 6-to-11 years, the weight on Day 1 will be used to calculate the mg/kg dose of study intervention.
- u. Blood samples for hematology and serum chemistry to be collected predose on dosing days. To include cystatin C in participants $<$ 18 years of age for calculation of eGFR. See Section **10.2** for the list of parameters.
- v. Blood samples for coagulation studies to be collected predose. Coagulation panel will include activated partial thromboplastin time (aPTT), prothrombin time (PT), and international normalized ratio (INR). Additional coagulation studies should be performed as clinically indicated.
- w. eGFR to be calculated as described in Section **8.2.4.1**.

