2.2.3. Clinical Overview

At present, no therapies are approved by regulatory authorities for the treatment of patients with PH. A number of supportive therapies are used in an attempt to mitigate some of the effects of the disease. Current medical management before renal failure develops is underpinned by hyperhydration with fluid intake recommendations of at least 3 liters per day per square meter of body-surface area (5 L/day for a 70-kg adult) ([Cochat et al., 2012](#)). These regimens can be problematic in infants and toddlers, necessitating placement of a gastrostomy tube to ensure adequate night-time fluid administration. Affected patients are at considerable risk of serious complications during periods of increased fluid loss (fever, diarrhea/vomiting, and urinary tract infections) or when oral hydration is compromised (following surgical procedures). Oral

potassium citrate administration is used to inhibit crystallization and alkalinize the urine. Treatment with vitamin B6 is effective in decreasing Uox in approximately 10% to 30% of patients with PH1 with certain *AGXT* mutations but has not been proven effective in treating other forms of PH ([Salido et al., 2012](#); [Hoppe et al., 2009](#); [Hoyer-Kuhn et al., 2014](#)).

For patients with more advanced disease, dialysis may be used in an attempt to remove endogenously over-produced oxalate. In contrast to the more typical 3-times-weekly hemodialysis regimens used in other types of renal failure, patients with PH may require hemodialysis 6 or 7 days per week. Given the limitations of dialysis and the inability to substantially impact oxalate over-production in most patients with PH1, most centers now consider liver transplantation approaches earlier in the disease course to minimize the risk of irreversible tissue damage. Other treatments include renal transplantation or, in patients with PH1, combined liver and kidney transplantation ([Nolkemper et al., 2000](#); [Rogers et al., 2001](#)). As with organ transplantation in other diseases, these procedures are associated with significant medical risk and a requirement for long-term treatment with immunosuppressive drugs that are also associated with significant side effects.

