5. STUDY POPULATION

5.1. INCLUSION CRITERIA

In order to be eligible to participate in this study, an individual must meet all of the following criteria:

Age

1. At least 6 years of age, at the time of signing the informed consent/assent

Type of Participant and Disease Characteristics

2. Documented diagnosis of PH1 or PH2, confirmed by genotyping (historically available genotype information is acceptable for study eligibility)
3. 24-hour Uox excretion ≥ 0.7 mmol (adjusted per 1.73 m^2 BSA in participants < 18 years of age) in both collections performed in the screening period. At least 12 participants must have at least one 24-hour Uox excretion ≥ 1.6 mmol (adjusted per 1.73 m^2 BSA in participants aged < 18 years).
4. Less than 20% variation between the two 24-hour urinary creatinine excretion values obtained in the screening period. Individuals who do not achieve $< 20\%$ variation between the 2 screening values may undergo a second round of urine collection. An extra 7 calendar days may be added to the screening window for participants to complete a second round of urine collection. Should potential participants again fail to achieve the within-20% variation, they will be excluded from participation.
5. Estimated GFR at screening ≥ 30 mL/min normalized to 1.73 m^2 BSA, calculated using the CKD-EPI equation in participants aged ≥ 18 years ([Levey & Stevens, 2010](#)) or the multivariate equation by Schwartz in participants aged 6 to 17 years ([Schwartz et al., 2012](#))

Sex

6. Male or female

Male participants:

A male participant with a female partner of childbearing potential must agree to use contraception, as detailed in Section 10.4.2, during the treatment period and for at least 12 weeks after the last dose of study intervention and refrain from donating sperm during this period.

Female participants:

A female participant is eligible to participate if she is not pregnant (see Section 10.4.1), not breastfeeding, and at least 1 of the following conditions applies:

Not a woman of childbearing potential (WOCBP) as defined in Section 10.4.1

OR

A WOCBP who agrees to follow the contraceptive guidance in Section 10.4.2 during the treatment period and for at least 12 weeks after the last dose of study intervention.

Contraceptive use by men or women should be consistent with local regulations regarding the methods of contraception for those participating in clinical studies.

Informed Consent/Assent

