A.3. 24-HOUR URINE COLLECTIONS

As urinary oxalate (Uox), determined from 24-hour urine collections, is the primary endpoint of the study, participants are encouraged to continue collecting 24-hour urines as planned.

The window for repeat collection of 24-hour urine samples that violate completeness criteria will be extended from 10 days to 14 days due to issues with courier availability and shipping issues across borders.

A.4. SAFETY LABORATORY TESTING

Hematology and serum chemistry are the essential laboratory tests for the evaluation of safety.

- 1) For both at-home and in-clinic visits, should delays or difficulties arise with the use of the central laboratory, a local laboratory may be utilized to monitor participant safety.
 - a. Should the use of a local laboratory be required, the collection of samples for the testing of coagulation parameters, cytokines, and complement may be omitted.

A.5. PROTOCOL DEVIATIONS

Dicerna recognizes that there may be minor protocol deviations for visits and assessments that fall outside of the protocol-specified windows. These should be continued to be documented as minor deviations.

A.6. INFORMED CONSENT

All participants who will undergo virtual site visits must provide their consent to the change in their participation. If provision of in-person written consent is not possible, consent may be provided to the Investigator (or designee) orally, over the telephone. This consent must be documented by the Investigator.

A.7. SPONSOR RISK ASSESSMENT

Primary Hyperoxaluria Types 1 and 2 are both serious and life-threatening diseases which ultimately may lead to kidney or combined kidney-liver transplantation. There are no approved therapies available and current supportive therapy consists of hyperhydration and alkalization of urine.

In Study DCR-PHXC-101, a single dose of 3 mg/kg DCR-PHXC (also called nedosiran), was shown to substantially lower Uox (mean 67%, range 42-80%) in participants with PH1 or PH2. As the magnitude of Uox levels has been shown to correlate with the risk of developing renal complications ([Zhao et al., 2016](#)), a lowering of Uox might potentially be of clinical benefit for patients with PH1 or PH2.

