#### 3.2. Sample Size and Power

Approximately 40 participants will be screened to achieve an estimated total of 36 evaluable participants.

For the sample size calculations, the primary endpoint of  $AUC_{24\text{-hour } U_{ox}}$  from Day 90 to Day 180 based on percent change from baseline was used. The group sequential design with pre-specified alpha spending for interim analysis and final analysis was utilized. The randomization ratio is 2-to-1 (active-to-placebo). The primary hypothesis to be tested is a one-sided superiority hypothesis at the significance level of 0.025. The  $AUC_{24\text{-hour } U_{ox}}$  in the placebo arm is assumed to be 0, as the  $U_{ox}$  values may oscillate up and down from baseline due to measurement variability. The  $AUC_{24\text{-hour } U_{ox}}$  in the active arm is assumed to be 3600 based on a 40% decrease over the 90 days. The effect size is assumed to be 1.2. Under these assumptions, the sample size of 36 patients (24 in the active arm and 12 in the placebo arm) will yield a power of approximately 94%. All calculations were performed using [REDACTED].

The above sample size calculation was performed under the assumption that there may be an interim analysis to re-estimate sample size after two-thirds of participants complete the study. However due to late enrollment experienced in the study, an interim analysis will not be performed.

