## 9.2. Clinical Laboratory Evaluations

Descriptive summaries for safety laboratory assessments will be presented at each visit starting at baseline. Changes from baseline to each post baseline visit will also be presented for continuous outcomes.

Baseline for safety laboratory assessments will be identified as defined in Section 6.1.2 regardless of whether an evaluation was scheduled, retested, or unscheduled. Since laboratory retests can occur for individual parameters, it will be necessary to define the baseline and all subsequent visit-specific laboratory values individually for each parameter.

[figure not shown]
In the case where below the limit of quantitation (BLQ) results are observed, and the LLOQ value is known, the BLQ values will be included in the numeric summary as the reported LLOQ value. In for those lab results reported as '<x' where x is numeric value, descriptive summaries will impute x as the lab result.

The following imputation rules will be applied to safety laboratory results where LLOQ value is unknown:

[figure not shown]
- If the patient has quantifiable concentrations of that analyte from other study visits, BLQ results will be imputed as  $\frac{1}{2}$  of the patient's lowest concentration for that analyte
- If the patient does NOT have any quantifiable concentrations of that analyte from other study visits, BLQ results will be imputed as  $\frac{1}{2}$  of the lowest concentration of that analyte based on all quantifiable results within the patient's dosing group/cohort

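### Setting 24-hour Uox to 0 at low oxalate concentrations, whatever the urine volume, can modestly overstate the reduction in active-arm responders; the test itself is essentially unaffected

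*SAP*

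**What the plan says.** SAP section 6.1.6 contains two rules. The first is "If a reported Uox measurement is below the limit of quantification (LLOQ), then the 24 hour Uox value will be imputed as 0". The second is "For oxalate values < 50 umol/L, the 24 hour Uox value will be imputed as 0 umol/24h". Neither mentions urine volume, and the section does not say whether 50 µmol/L is the LLOQ.

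Under SAP section 6.1.9 the primary AUC is a trapezoid over percent changes from baseline, so a value of 0 enters as a 100% fall. Section 6.1.5.2 averages the results when a visit has more than one valid collection; a zero would then be diluted. None of the sensitivity analyses for the primary endpoint in section 8.5 varies the zero rule.

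For safety laboratory results with a known LLOQ, SAP section 9.2 says that "the BLQ values will be included in the numeric summary as the reported LLOQ value". If the LLOQ is unknown, it uses half of a lowest quantified concentration.

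Protocol section 1.3, footnote p, says: "Participants should maintain consistent fluid intake (i.e., hyperhydration) over the course of the study". Protocol section 5.1 requires at least 0.7 mmol in both screening collections and adds: "At least 12 participants must have at least one 24-hour Uox excretion ≥ 1.6 mmol".

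**The concern.** Daily excretion is concentration times volume. In a trial whose participants are asked to drink heavily, a low concentration does not mean that excretion is close to nil: each litre just under 50 µmol/L carries almost 0.05 mmol. Zero is the lowest value that excretion can take, so it never understates a participant's reduction.

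Participants with little or no response are very unlikely to reach the cut-off, so the rule acts on one arm in practice. The estimates at stake are the primary AUC, the exploratory Day 1 to Day 180 AUC and the percent change at Day 180. If 50 µmol/L is above the LLOQ, the rule would also replace quantified results with 0.

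**Working it through.** **Planning figures.** SAP section 3.2 assumes an active-arm AUC of 3600, 24 versus 12 participants and about 94% power, and states: "The effect size is assumed to be 1.2". The normal approximation gives 1.2 × √(24 × 12/36) = 3.394; 3.394 − 1.960 = 1.434; power 92.4% (90.9% with a noncentral t on 34 df). That is close to the stated figure. The implied SD is 3600/1.2 = 3000, and the standard error of the difference is 3000 × √(1/24 + 1/12) = 1061.

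**One visit, adult at baseline 0.7 mmol.** Excretion at the cut-off is 0.05 × V mmol, where V is an assumed urine volume in litres. The maximum overstatement is 100 × 0.05V/0.7 percentage points. With visits at Days 90, 120, 150 and 180 the trapezoid weights are 15, 30, 30 and 15 days, so an interior visit is multiplied by 30.

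| V | Excretion at cut-off (mmol) | Maximum overstatement (points) | True fall needed | Interior visit, maximum AUC units |
|---|---|---|---|---|
| 2 L | 0.10 | 14.3 | 85.7% | 429 |
| 3 L | 0.15 | 21.4 | 78.6% | 643 |
| 4 L | 0.20 | 28.6 | 71.4% | 857 |
| 5 L | 0.25 | 35.7 | 64.3% | 1071 |

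**Who can be affected.** An unchanged adult at 0.7 mmol needs 0.7/0.05 = 14 L. With the BSA adjustment, a child needs 0.7/(0.05 × 1.73) = 8.1 L/m².

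**When the documented falls can trigger the rule.** Protocol Appendix A, section A.7, reports a mean fall of 67% (range 42-80%) after a single 3 mg/kg dose. The lowest excretion in that range is 0.7 × (1 − 0.80) = 0.14 mmol, so in adults the rule cannot apply below 0.14/0.05 = 2.8 L.

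**Bias in the active-arm mean.** Monte Carlo, 2,000,000 draws. Assumed baselines: one third uniform on 1.6-2.4 mmol and two thirds uniform on 0.7-1.6 mmol, the one third reflecting 12 of 36 participants. Three models for the fall:
- Clipped: normal, mean 67%, SD 11 points, values outside 42-80% moved to the limits. Mean AUC 5977.
- Truncated: the same normal, values outside 42-80% excluded. Mean fall 64.9%, so mean AUC 64.9 × 90 = 5841.
- Wider (assumed): normal, mean 67%, SD 15 points, clipped to 20-95%. Mean AUC 6014.

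Overstatement in AUC units under the zero rule (ranges are repeat runs):

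| V | Truncated | Clipped | Wider |
|---|---|---|---|
| 2 L | 0 | 0 | +25 |
| 3 L | +1 | +9 | +68 |
| 4 L | +46 to +47 | +88 | +148 to +149 |
| 5 L | +180 to +181 | +244 to +246 | +281 to +282 |

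The largest relative biases are 180/5841 = 3.1%, 246/5977 = 4.1% and 282/6014 = 4.7%. A separate simulation used lognormal baselines, variable volumes and within-participant variation. At a 67% mean fall it gave +9 to +327 units over 2-5 L, or 0.1 to 5.4% of the treatment difference.

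**Effect on the test.** Trials of 24 versus 12 were simulated with baseline-adjusted ANCOVA, a mean fall of 40% and a between-participant SD of 33 points. Power without and with the rule was 0.896 and 0.895 at 3 L, 0.901 and 0.900 at 4 L, and 0.890 and 0.889 at 5 L. With volumes spread over 2-5 L it was 0.902 and 0.899. The t statistic fell in 79-83% of affected trials, because the zeros also widen the active-arm spread. With no drug effect, one-sided type I error was 2.40% both ways at 3 L and 2.42% both ways at 5 L.

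**Key secondary endpoint.** Success is below 0.60 mmol. A value under the cut-off is already a success unless volume exceeds 0.60/0.05 = 12 L in an adult or 0.60/(0.05 × 1.73) = 6.9 L/m² in a child.

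**The case against.** The strongest reply is that nothing inferential is at risk and that the bias is conditional. Both parts stand. The largest figure in the table is 282/1061 = 0.27 of the planning standard error. No urine volumes are documented, and the 5 L/day in protocol section 2.2.3 is recommended intake, not output. With the documented falls the bias is nil at 2 L and negligible at 3 L.

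Four further points have weight:
- The difference from SAP section 9.2 might be read as a self-contradiction. It is not, because that section governs descriptive safety summaries. It shows only that the SAP uses non-zero substitutes elsewhere.
- The heading of section 6.1.6 suggests that 50 µmol/L is the LLOQ. If so, no quantified value is lost. The text does not say so.
- The rule would not be invisible. By-visit summaries of Uox by arm, with minima, and full listings are planned (SAP sections 4.1, 6.1.10 and 8.1). A minimum of 0 would show that it had applied, but not how far the estimate depends on it.
- A volume-based substitute is not closer to the truth for every value. Below 25 µmol/L, zero is closer than LLOQ × volume (18-32% of affected values in the wider model). Below 12.5 µmol/L, zero is also closer than LLOQ/2 × volume.

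**Conclusion.** The point holds as a minor issue of estimation. The rule ignores volume, errs only towards benefit in an affected participant, and acts almost only on active-arm responders. With the documented falls, the active-arm mean AUC is overstated by roughly 0 to 4% for volumes of 2-5 L; with an assumed wider spread of falls, by 0.4 to 4.7%. One participant at baseline 0.7 mmol and 5 L could be overstated by up to 36 points at a visit. These sizes rest on assumed volumes, baselines and shapes for the distribution of falls.

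A reader might infer that the rule makes a false-positive result more likely, helps the trial reach significance, or raises the normalization rate. The documents do not support any of these. The rule is the same in both arms, so with no drug effect both arms are treated alike. In the simulations it slightly lowers the t statistic more often than not. The key secondary thresholds lie well above what the rule can alter at plausible volumes.

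**What to change.** Amend SAP section 6.1.6 before unblinding:
1. State whether 50 µmol/L is the assay LLOQ. If it is not, use the quantified concentration times that collection's volume.
2. For values below the LLOQ, replace 0 with LLOQ/2 × that collection's volume, then apply the BSA adjustment where required.
3. Run zero and LLOQ × volume as sensitivity analyses for the primary endpoint.
4. Report the number of affected values by arm and visit.

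If 50 µmol/L is the LLOQ, the group-mean bias in AUC units at 2 / 3 / 4 / 5 L would be:

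| Model | Zero | LLOQ/2 × volume | LLOQ × volume |
|---|---|---|---|
| Clipped | 0 / +9 / +88 / +244 | 0 / +4 / +37 / +95 | 0 / 0 / −13 / −55 |
| Wider | +25 / +68 / +148 / +281 | +6 / +14 / +32 / +62 | −12 / −39 / −85 / −158 |

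In both models LLOQ/2 × volume has a smaller mean bias than zero wherever values are affected. LLOQ × volume does better in the first model and worse in the second, which is why it belongs among the sensitivity analyses.

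The cost is a short SAP edit and one or two extra runs. Collection volume is not listed in protocol Table 2, but any result in mmol/24 h already requires it. The reported effect may be slightly smaller.
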